9. SECONDARY ANALYSES

9.1 Secondary Efficacy Outcome measures

In addition to the primary outcome, several secondary analyses will be conducted. We will examine changes in types of naming errors (defined by the PNT) by tDCS treatment group. The Cinderella story will be analyzed by comparing lexical diversity (VOCD) for nouns, verbs and adjectives; number and types of errors; length and patterns of pauses by treatment group. Pre and post comparisons with both non-aphasic and aphasic speakers from the AphasiaBank database who share a number of demographic features (e.g., type and severity of aphasia, age, etc) will also be made.

At the end of the study, for the interval scale variables, mean change from baseline to immediate post-testing in secondary outcome measures will be reported by treatment group along with the 95%

confidence intervals. Treatment comparisons will be made with a paired *t*-test. For binary variables, the proportion of subjects immediately post-testing will be reported by treatment group along with the 95% confidence intervals.

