2.2.4 Procedures for the Computerized Naming Assessments (Visits 2, 3, 19-24)

The following procedures will be performed during Visits 2, 3, and 19-24:

1. Turn on the laptop computer and position in front of the patient
2. Set up and start internal web-camera for audio-visual recording.
3. Administer the combined *Philadelphia Naming Test* (PNT; Roach et al., 1996) on a laptop computer. *Note to clinician: The PNT (175 items) will also include 80 treated pictures for a total of 255 picture presentations:*
 - Instruct the patient to overtly name each picture as soon as it is displayed
 - Trials will end following a response or after 20-seconds have elapsed, in which the administrator will say the correct picture name in order to discourage perseveration on subsequent trials
4. Stop web-camera and save video file for later scoring of naming.

2.2.5 Procedures for the “Cinderella Story” picture discourse analysis (Visits 3, 19, 21, and 23)

The following procedures will be performed during Visits 3, 19, 21, and 23:

[figure not shown]
1. To be completed following the administration of the CNA-PNT, so the laptop computer and web-camera set-up will need to remain for this portion of the assessment
2. Place the picture book in front of the patient
3. Tell the patient, "I'm going to ask you to tell a story. Have you ever heard the story of Cinderella?" (Make note of answer) "Do you remember much about it? These pictures might remind you of how it goes. Take a look at the pictures and then I'll put the book away, and ask you to tell me the story in your own words." Allow the patient to look through the book (assist with page turning, if needed) and then, if necessary, prompt: "Now tell me as much of the story of Cinderella as you can. You can use any details you know about the story, as well as the pictures you just looked at." Continue until the patient concludes the story or it is clear s/he has finished.
4. Stop web-camera and save video file for later transcription

[figure not shown]

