8.4 Multiplicity

Since this is a phase II study, the false positive error rate has been relaxed (Schoenfeld 1980). For a futility design the type I and type II error rates are reversed as compared to a traditional, superiority hypothesis. For the primary analysis, the probability of incorrectly declaring a drug futile is 0.1 (or 10%, type I error is the false negative rate). Given that the active tDCS comes from a distribution with a mean change of the control group (e.g. the treatment is like the sham change), the probability of incorrectly moving to a Phase III trial is 0.15 (or 15%, type II error is the false positive rate).

For secondary outcomes and safety analyses, no adjustment of Type I error probability will be considered, since they will be treated as exploratory.

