9.3 Post-Testing Phase

The longer follow-up post-testing phase will provide exploratory information on whether the immediate post-testing improvement after 3 weeks of treatment can be sustained. The mean (95% CI) changes from baseline to immediate (within 1 week) post-testing, 4 weeks post-testing and 6 months post-testing will be reported. Box and whisker plots will be produced to show the distribution of naming accuracy over time by group.

To explore the longitudinal data, a Repeated Measures model (SAS® MIXED procedure with REPEATED sub-command) will be constructed by tDCS group. The model will include the following fixed effects: visit (as a classification variable), aphasia type, severity, and clinical center as independent variables. Various error structures will be examined (e.g., compound symmetry, autoregressive, unstructured), and the final structure will be selected based on the model Akaike Information Criteria. A similar modeling approach may be applied to other secondary outcomes (e.g., number of naming errors).

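### Cinderella-story errors are compared as a number although the story has no set length, so a difference between arms in the count cannot be read as a difference in accuracy

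*SAP*

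**What the plan says.** SAP 9.1 and Protocol 3.5.1 use the same wording for the Cinderella outcomes. After lexical diversity they name "number and types of errors; length and patterns of pauses by treatment group". The word length there describes the pauses, not the story. For interval-scale variables both sections add that "mean change from baseline to immediate post-testing in secondary outcome measures will be reported by treatment group", with 95% confidence intervals. Neither section gives a denominator, an offset or a length covariate for the errors, and neither says whether fewer errors counts as improvement.

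Protocol 2.2.5 describes how the story is collected, once at each of Visits 3, 19, 21 and 23. The prompt is "Now tell me as much of the story of Cinderella as you can". The instruction to the clinician is "Continue until the patient concludes the story or it is clear s/he has finished". The last step is "Stop web-camera and save video file for later transcription". No time limit, word limit or truncation of the transcript is described.

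The picture-naming assessment differs on this point: "The PNT (175 items) will also include 80 treated pictures for a total of 255 picture presentations" (Protocol 2.2.4).

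On status, SAP 8.4 and Protocol 3.4.4 say of secondary outcomes that "no adjustment of Type I error probability will be considered, since they will be treated as exploratory".

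**The concern.** When the amount of speech is left to the patient, a number of errors measures two things at once: how much was said and how often it was wrong. In aphasia both may change with recovery, and the amount said may itself respond to treatment. If active stimulation led patients to say more, their error count could rise relative to sham while their accuracy improved. If it led them to say less, the count could fall with no gain in accuracy.

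Randomisation and the use of change from baseline do not remove this. The length of the follow-up story is fixed after randomisation and can differ between arms because of treatment. Even where treatment leaves length alone, variation in length from one telling to the next adds noise to a measure taken once per time point.

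In the listed procedures, the story is the only connected-speech sample taken after treatment. A reader looking for support beyond single-picture naming would turn to it, and a count in the wrong direction could be taken as contradicting the naming result.

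**Working it through.** The documents give no power, effect size, story length or error rate for this outcome, so there is no figure of the plan to reproduce. The check is algebra plus an illustration over an assumed range.

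**Inputs**
- Outcome: a number of errors, with no denominator (SAP 9.1, Protocol 3.5.1).
- Story length: free (Protocol 2.2.5).
- Assumed for illustration: 100 words and 20 errors per 100 words at baseline, length multiplied by 1.25 to 2, error rate multiplied by 0.4 to 1.

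**Formula**
- Count = words × error rate.
- If length is multiplied by g and the error rate by r, the count is multiplied by g × r.
- The count rises when g × r > 1. With g > 1, it rises unless the rate falls by at least 1 − 1/g.

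**Break-even fall in the error rate**

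| Length factor g | Count at unchanged rate (baseline 20) | Fall in rate at which the count stops rising |
|---|---|---|
| 1.25 | 20 × 1.25 = 25 (+25%) | 1 − 1/1.25 = 20% |
| 1.5 | 20 × 1.5 = 30 (+50%) | 1 − 1/1.5 = 33% |
| 2 | 20 × 2 = 40 (+100%) | 1 − 1/2 = 50% |

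The break-even falls depend only on g. The assumed baseline of 100 words and 20 errors does not enter them.

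**Count and rate side by side**

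| Change | Words | Errors per 100 words | Error count |
|---|---|---|---|
| Length × 1.5, rate down 20% | 100 → 150 | 20 → 16 | 20 → 150 × 0.16 = 24 |
| Length × 2, rate down 25% | 100 → 200 | 20 → 15 | 20 → 200 × 0.15 = 30 |
| Length × 2, rate down 60% | 100 → 200 | 20 → 8 | 20 → 200 × 0.08 = 16 |

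In the first two rows accuracy improves and the count rises. In the third row the fall in rate exceeds the 50% break-even, so the count falls too. The relation also runs the other way: a story half as long (g = 0.5) gives a lower count unless the error rate at least doubles (1/0.5 = 2).

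**The case against.** The strongest reply is that SAP 9.1 and Protocol 3.5.1 list domains and do not define variables. Neither says raw count, neither rules out normalising, and SAP section 2 promises an update before database lock. That is fair as far as it goes. But number is the only unit given, nothing elsewhere supplies another, and the promised update is an occasion to settle the point, not evidence that it is settled.

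A second reply is that a randomised comparison of counts validly estimates the effect on counts, and that errors per 100 words also depends on speech produced after treatment. Both statements are true. The difficulty is interpretation: the count alone cannot separate more speech from less accurate speech. Because the rate has its own weakness, it should be shown with the counts and total words and should not replace them.

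Three stronger readings are tempting, and the documents do not support them.

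- A reader might infer that a patient who tells a longer story is always scored as worse. That follows only when g × r > 1. It also assumes that fewer errors is the good direction, which the plan implies but does not state.
- A reader might extend the point to naming errors, since a picture trial can end in silence. The naming test has a fixed number of presentations, and both documents take the error types from the PNT, whose scoring scheme is not reproduced. One silence that becomes one wrong word adds to one error type only. The SAP 9.3 sentence "A similar modeling approach may be applied to other secondary outcomes (e.g., number of naming errors" is permissive. Dividing by attempted items would bring in a denominator that treatment can change.
- A reader might infer that the trial's conclusion is at risk. The decision rule in SAP 8.2 and Protocol 3.4.2 uses only the change in correctly named items.

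**Conclusion.** The point holds for the Cinderella error measure. As written, the outcome confounds amount of speech with accuracy, so a difference between arms in the count cannot be read as a difference in accuracy. It can point the opposite way from accuracy whenever the proportional growth in story length outweighs the fall in error rate.

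The mechanism needs no assumed value, but its size in this trial is unknown. The thresholds of 20%, 33% and 50% rest on assumed length factors of 1.25, 1.5 and 2. How often patients would cross them cannot be judged from the documents.

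The reach is limited to one exploratory secondary outcome. Lexical diversity and pauses come from the same story and are not assessed here. The change is worth making because it is cheap and because a denominator chosen after unblinding would be open to the charge of selective reporting.

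**What to change.** In Protocol 3.5.1 and SAP 9.1:

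- Define the Cinderella error outcomes, in total and by type, as errors per 100 words from the same transcript. Alternatively, use a count model with log(words) as offset. Name one of the two as the planned analysis.
- Report total words and raw error counts by arm beside it at each time point.
- State which direction is improvement.
- Say how a story with no scorable words is handled, since neither the rate nor the offset exists for it.

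The cost is wording in two sections and a word count from transcripts that are already planned. No new visit, test or patient is needed, and the SAP update before database lock is a natural place for the change.

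The downside is that rates are unstable for very short stories: one error moves the rate by 100/words, which is 1 per 100 in a 100-word story and 2.5 per 100 in a 40-word story. Rates also condition on how much the patient says after treatment. Showing counts and words alongside lets the reader see both.

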9.2 Exploratory Analyses of the Primary Outcome measures

Spearman's correlation coefficients will be computed for pre-post change in anomia versus aphasia type first using all patients and then by tDCS group. This association will be further explored using the longitudinal data in a GLMM model described in section 3.14 (post-testing phase). Since there will be little statistical power to detect an interaction of aphasia type and treatment, we will examine the main effect of aphasia type (adjusting for the other covariates) by tDCS group.

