2.2.2 Procedures for Diagnostic Testing (Visit 1)

If the patient passes the screening portion, diagnostic testing will be conducted during the same visit. The following diagnostic testing procedures will be performed:

1. Administer the *Western Aphasia Battery-Revised* (WAB-R):
 - o The WAB-R will characterize the patients' overall language impairment through the evaluation of the main clinical aspects of language functioning, including speech content, speech fluency, auditory comprehension, repetition, and naming. The WAB-R allows for the differentiation of these specific language abilities, as well as the classification of aphasia type. The WAB-R also yields a composite score, the Aphasia Quotient, which provides an overall measure of severity, in which lower scores denote more severe aphasia (Kertesz, 2007). Speech-language pathologists (SLPs) will refer to the manual for explicit instructions regarding administration and scoring procedures. Administration time will range between 30-45 minutes.
2. Administer the *Boston Naming Test-Second Edition* (BNT):
 - o The BNT represents a measure of object naming abilities from a corpus of 60 line drawings. Object names are ranked along a continuum, with easier, more higher-frequency words appearing at the beginning of the test and more difficult, lower-frequency words appearing near the end. To eliminate patient frustration, the BNT implements a ceiling effect so that once the patient incorrectly names eight items in a row, testing will cease, with the assumption that (s)he would not correctly name the upcoming, more difficult words (Kaplan, Goodglass, & Weintraub, 2001). SLPs will refer to the manual for explicit instructions regarding administration and scoring procedures. Administration time will range between 5-20 minutes.
3. Administer Subtest 6 from the *Apraxia Battery for Adults-Second Edition* (ABA-2):

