8.3 Sample Size Determination

In preliminary studies, the mean difference in change from baseline in the active and sham groups in naming accuracy was ~2.5 points (Baker, Rorden, & Fridriksson, 2010, Fridriksson et al., submitted). In one study, the S-tDCS (sham) group improved ~1.2 point from baseline to 1 week (Baker, Rorden, &

Fridriksson, 2010). In another study, the S-tDCS group improved ~3.9 points from baseline to 1 week (Fridriksson et al., submitted). For power calculations, we assumed the mean change from baseline to immediate (1 week) post-testing for the A-tDCS group under the null hypothesis of non-futility is equal to $\mu_s + \delta = 4 + 1.5 = 5.5$. When the sample size is 33 per group, a two sample t-test with a 0.10 one-sided significance level will have 85% power to reject the null hypothesis that the A-tDCS treatment is 1.5 points better than S-tDCS (sham) and declare futility when the A-tDCS treatment comes from a distribution with mean change of 4 (assuming the pooled SD is 2.6). As with most clinical studies, a certain amount of drop-outs (including subject withdrawal or lost-to-follow-up) can be expected. In preliminary studies less than 5% of visits were missing. Conservatively assuming the drop-out rate to be no more than 5% over 5 weeks, the required sample size was inflated from 33 to 37 per intervention arm to account for the effect of the drop-outs in the intent-to-treat analysis using an inflation factor (Friedman, et al, 1985).

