9.4 Exploratory Analyses of BDNF polymorphism

A two group *t*-test with a 0.05 two-sided significance level will have 80% power to detect a difference in mean reaction time of 2.6, assuming that the common standard deviation is 2.6, when the sample sizes in the two allele groups are 12 having at least 1 MET allele and 25 without the MET allele, respectively (a total sample size of 37 patients in the A-tDCS group assuming 33% have at least 1 MET allele).

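### SAP 9.2 plans a Spearman coefficient against aphasia type, an unordered classification, so with more than two types the result depends on how they are numbered; separately, SAP 9.4 states power for an endpoint that neither document defines

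*SAP*

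**What the plan says.** SAP 9.2 states that Spearman's "correlation coefficients will be computed for pre-post change in anomia versus aphasia type first using all patients and then by tDCS group". It then says the association will be explored further in the longitudinal model, and that "we will examine the main effect of aphasia type (adjusting for the other covariates) by tDCS group".

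Protocol 2.2.2 describes what the WAB-R yields. It separates specific language abilities, "as well as the classification of aphasia type". It also gives the Aphasia Quotient (AQ), "which provides an overall measure of severity, in which lower scores denote more severe aphasia". So the AQ has a stated direction and type does not. The randomization sections (Protocol 3.2, SAP 6) and the longitudinal model (SAP 9.3) also list type and severity as separate variables. No section gives the types an order, a coding or a number of levels.

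SAP 9.4 consists of one power statement for the BDNF comparison: a two-sided 0.05 t-test has "80% power to detect a difference in mean reaction time of 2.6, assuming that the common standard deviation is 2.6", with 12 and 25 patients in the two allele groups ("a total sample size of 37 patients in the A-tDCS group assuming 33% have at least 1 MET allele"). It gives no unit and names no other BDNF endpoint.

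**The concern.** Spearman's coefficient correlates ranks, so both variables must at least be ordered. If type is unordered, the analyst has to number the categories before a rank exists, and the coefficient then describes that numbering as much as the data. With three or more types, two analysts following SAP 9.2 faithfully could report different coefficients and p-values from the same data set. SAP 2 says that the SAP will define all pre-specified analyses; here the choice that determines the answer is left open.

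In 9.4, a reader cannot tell which variable will be compared between the allele groups, or in what unit. The primary outcome is a count of correctly named items (SAP 8.1). The secondary outcomes are naming-error types and measures from the Cinderella story (SAP 9.1). Neither list includes a reaction time.

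**Working it through.** **1. Coding dependence, by hand.** Suppose equal-sized types. The numerator of a correlation between code and type mean is the sum over types of (code - mean code) x (type mean - overall mean).

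- Four types, means 2.5, 3.5, 4.5, 5.5 (overall 4), codes averaging 2.5:
  - codes 1, 2, 3, 4: 2.25 + 0.25 + 0.25 + 2.25 = 5
  - codes 4, 3, 2, 1: -5
  - codes 3, 1, 4, 2: -0.75 + 0.75 + 0.75 - 0.75 = 0
- Three types, means 3, 4, 5 (overall 4), codes averaging 2:
  - codes 1, 2, 3: 1 + 0 + 1 = 2
  - codes 2, 1, 3: 0 + 0 + 1 = 1, so the association is halved but not removed
- Two types: recoding can only reverse the sign.

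**2. Size, by simulation.** From the documents: 74 patients in total (SAP 4) and an SD of 2.6 (SAP 8.3). Assumed: the group sizes, the type means, a normal outcome, and 2.6 as the SD within each type. Each scenario has 20,000 simulated trials, with every code order applied to each data set and the Spearman p-value from the t approximation on 72 degrees of freedom.

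| Types (sizes) | Assumed mean changes | Mean coefficient over codings | Chance of p<0.05 over codings | Kruskal-Wallis |
|---|---|---|---|---|
| 4 (19/19/18/18) | 2.5, 3.5, 4.5, 5.5 | -0.39 to +0.39 | 3.8% to 94.5% | 84.7% |
| 3 (25/25/24) | 3, 4, 5 | -0.30 to +0.30, never closer to zero than about 0.14 | 23.0% to 73.7% | 62.1% |
| 2 (37/37) | 3, 5 | -0.36 or +0.36 | 88.9% either way | not needed |

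With four types and no true difference, any one order fixed in advance keeps its error rate at about 5%. If the order is left open, at least one of the 24 orders reaches p<0.05 in 23.4% of trials.

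**3. The power figure in SAP 9.4.** Inputs, all from 9.4: difference 2.6, SD 2.6, groups of 12 and 25, two-sided alpha 0.05.

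- Group split: 0.33 x 37 = 12.2, which agrees with 12 and 25.
- Standard error: 2.6 x sqrt(1/12 + 1/25) = 0.913.
- Normal approximation: 2.6/0.913 - 1.96 = 0.89, giving 81.3%.
- Exact noncentral t, 35 degrees of freedom: 79.1%.

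The stated 80% is reproduced. The difference equals one SD (2.6/2.6 = 1), so the power holds whatever the unit; the gap is the endpoint itself.

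**4. Search for a reaction time.** The term occurs only in SAP 9.4. For the naming test, Protocol 2.2.4 says "Trials will end following a response or after 20-seconds have elapsed", which sets a limit but describes no timing of responses. For the treatment task, Protocol 2.2.8 describes a saved file of responses and a displayed accuracy score. The Cinderella analysis in SAP 9.1 includes length of pauses, but does not call that a reaction time.

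**The case against.** **The number of types is unknown.** Type is a balancing factor in a 74-patient randomization, so a coarse grouping, even into two, is not excluded. This stands, and the point is therefore conditional: with two types nothing but the sign is arbitrary.

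**The illustration is generous.** The four assumed means span 3.0 points, twice the 1.5-point margin. Moreover, SAP 8.3 gives 2.6 as a pooled SD for a two-arm comparison without adjustment for type, so spread between types may already be inside it. The between-type variance of the assumed means is 5/4 = 1.25; adding it gives sqrt(6.76 + 1.25) = 2.83 within an arm. This also stands. The simulation covers only all 74 patients, whereas 9.2 also plans the coefficient within each tDCS group. The figures show the mechanism, and a reader should not take 4% to 95% as this trial's risk.

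**The adjusted main effect already answers the question.** A reader might infer from the Spearman plan that the aphasia-type question is lost. The documents do not support that, because 9.2 also plans an adjusted main effect of type. This does not repair the coefficient, which would still be reported. Nor is the model fully specified: SAP 9.3 marks only visit as a classification variable. That silence does not show that type would enter as a numeric score, since clinical center is not marked either. But it should be settled in the text.

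**The 9.4 endpoint may exist.** Latencies could perhaps be recovered from the recordings or response files, but neither document says so. Because the 9.4 SD equals the naming-change SD in SAP 8.3 ("assuming the pooled SD is 2.6"), a reader might infer that reaction time is a slip for change in naming. The match is suggestive, not proof. A reader might also object that a comparison within the active arm cannot show modification of the tDCS effect. SAP 9.4 makes no such claim: it says the comparison lies in the A-tDCS group and calls it exploratory.

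**Conclusion.** The point holds as a minor one. SAP 9.2 names a statistic that does not suit the variable as described. Provided that more than two types are used and they have no natural order, its size, sign and p-value depend on an arbitrary numbering. How much depends on the number of types and how far they differ: in the assumed four-type case the association can vanish, and in the three-type case it is roughly halved at worst. SAP 9.4 leaves its endpoint undefined, while its power arithmetic is correct. Neither matter reaches the primary analysis: SAP 9.2 and 9.4 are headed exploratory, and the futility decision rests on the comparison in SAP 8.2.

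**What to change.** - **SAP 9.2:** replace the Spearman coefficient with an order-free comparison of pre-post change across aphasia types, for all patients and by tDCS group. Kruskal-Wallis, or a linear model with type as a categorical factor, would serve. State the categories to be used.
- **SAP 9.3:** declare aphasia type a classification variable. Section 9.2 refers to this model as section 3.14, a number the SAP does not contain; the bracketed title there points to 9.3, so correct the reference too.
- **SAP 9.4:** the sponsor should name the BDNF endpoint and its unit. The power figure can stay if the one-SD difference is still intended.

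These are changes of wording, and SAP 2 already provides for an update before database lock and unblinding. The one statistical cost is in 9.2. If the types do have a natural order, Spearman in that order is more powerful: 94.5% against 84.7% in the four-type illustration, and 73.7% against 62.1% with three types. If the investigators hold that such an order exists, they could keep Spearman by writing the order into the SAP before unblinding.

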4. STUDY DESIGN AND OBJECTIVES

At total of 74 subjects from 2 sites will be randomized 1:1 to tDCS (n=37) or sham (n=37). This study design will allow us to assess whether it is futile to proceed with further study of tDCS in a larger Phase III trial.

The primary objective of the study is to compare tDCS versus sham-control in stroke patients with aphasia in order to assess whether it is futile to proceed with further study of tDCS.

Planned enrollment duration: approximately 4 years (0.77 patients /site/month)

Duration of follow-up in Primary Study Phase: 3 weeks

Duration of follow-up in Secondary Study Phase: 7 weeks from baseline

Duration of follow-up in Post-testing phase: 27 months from baseline

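### SAP 9.2 replaces the aphasia-type-by-treatment interaction with separate aphasia-type effects in each arm, so no planned analysis estimates whether the tDCS effect differs by aphasia type

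*SAP*

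**What the plan says.** SAP 9.2 raises the interaction and sets it aside: "Since there will be little statistical power to detect an interaction of aphasia type and treatment", the plan continues, "we will examine the main effect of aphasia type (adjusting for the other covariates) by tDCS group". The Spearman correlations of naming change with aphasia type, in the same section, are computed "first using all patients and then by tDCS group".

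Section 9.2 refers onward to a longitudinal model in a section 3.14, which the SAP does not contain; the post-testing model is in 9.3. That model "will be constructed by tDCS group", with fixed effects "visit (as a classification variable), aphasia type, severity, and clinical center as independent variables". Protocol 3.5.2 has the same structure, with time in place of visit. Neither list contains a treatment term or a type-by-treatment term.

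The treatment descriptions in protocol 2.1 and 2.2.8 give the computerized naming task to every patient; the arms differ only in whether the stimulation is active or sham. SAP 8.4 treats secondary outcomes as exploratory, without adjustment of the type I error.

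**The concern.** Whether the effect of tDCS depends on aphasia type is a question about the tDCS-minus-sham difference across types. The planned analysis instead asks, in each arm, whether patients of different types change by different amounts. Some types may improve more with training whatever the stimulation, and a type effect in the active arm would then appear even if tDCS did nothing.

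Low power is a good reason to call an interaction estimate imprecise. It does not justify replacing it with two analyses of half the sample each, because the contrast between those two analyses carries the same imprecision, now unreported. Two by-arm results printed side by side, without an estimate of their difference or a caution, also invite the reader to conclude that type matters under tDCS but not under sham because one p-value is below 0.05 and the other is not.

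**Working it through.** **Inputs.** 37 patients per arm (SAP 4); SD of change 2.6 and evaluable n of 33 per arm (SAP 8.3); margin 1.5 points (SAP 8.2).

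**Assumptions, not in the documents for this analysis.** Two-sided 0.05 tests (9.2 gives no level; 0.05 two-sided is borrowed from SAP 9.4); two aphasia types split 18/19 in each arm, with other splits as a check; the same SD in every type and arm; covariates ignored.

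**Step 1: the plan's own figure.** No power is stated for the aphasia-type analyses, so the check is on SAP 8.3: "When the sample size is 33 per group", "a two sample t-test with a 0.10 one-sided significance level will have 85% power". By the normal approximation, n = 2 × (2.6/1.5)² × (1.2816 + 1.0364)² = 2 × 3.004 × 5.373 = 32.3, so 33 per arm. Noncentral t power at 33 is 85.2%. The figure reproduces, so the SD is usable below.

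**Step 2: does splitting by arm help precision?**
- Within-arm SE of the type effect: 2.6 × √(1/18 + 1/19) = 0.855 points.
- SE of the difference between the two arms' type effects: 2.6 × √(2/18 + 2/19) = 1.21 points, which is √2 × 0.855.

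The same SE applies to the interaction in one model, so nothing is gained. For a 1.5-point effect, within-arm power is 40% and interaction power 23%. The within-arm figure is higher because it tests a different hypothesis: that type has no effect in that arm.

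**Step 3: how often would the arms disagree by chance?** Let the true type effect be identical in both arms and p the power of each within-arm test. The arms are independent, so P(significant in exactly one arm) = 2p(1-p), and P(significant in the active arm only) = p(1-p).

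| Common type effect (points) | p | Exactly one arm | Active only |
|---|---|---|---|
| 0 | 0.050 | 9.5% | 4.8% |
| 0.5 | 0.088 | 16% | 8% |
| 1.0 | 0.206 | 33% | 16% |
| 1.5 | 0.400 | 48% | 24% |
| 1.72 | 0.50 | 50% | 25% |
| 2.0 | 0.623 | 47% | 23% |
| 2.6 | 0.840 | 27% | 13% |
| 4.0 | 0.995 | 1% | 0.5% |

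The 50% maximum moves to 1.84 points with a 12/25 split and 2.01 points with 9/28. Simulation (40,000 trials) agrees with the table. One three-type scenario (effects 2.2, 1.1 and 0 points) gave 49% and one four-type scenario (2.4, 1.6, 0.8 and 0) gave 46%. In the same simulations a direct interaction test rejected in 4.9% to 5.1% of trials without an interaction.

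**Step 4: what a direct interaction estimate would deliver.** With the 18/19 split, the 95% CI half-width is about 2.4 points. Power is 23% for an interaction of 1.5 points and 53% for 2.5; 80% power needs about 3.4. With 12/25, the SE is 1.29, the half-width about 2.6, the powers 21% and 48%, and 80% needs about 3.6 points.

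**The case against.** The strongest reply is that the plan does not commit the error. Section 9.2 is headed exploratory, says only that the type effect will be examined, sets no significance level, and proposes no comparison of p-values between arms. It does not claim to identify who benefits, and it is open about low interaction power, which Step 4 confirms. All of this stands.

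Three stronger readings are therefore not supported:

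- **That the plan itself produces spurious arm differences half the time.** These arise only if someone runs 5% tests and reads discordance as a difference. Even then, 50% is a ceiling that needs aphasia type to be prognostic with within-arm power near 0.5. It counts both directions.
- **That this analysis would set eligibility for a Phase III trial.** Protocol 3.4.2 and SAP 8.2 tie the Phase III decision to the primary futility hypothesis. Nothing links it to 9.2.
- **That the by-arm analyses must be removed.** As descriptive summaries they do no harm, and with confidence intervals in both arms a reader could form a rough contrast.

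A technical reservation also stands. Separate models let the severity and center effects and the residual variance differ by arm. The difference between by-arm estimates therefore equals the interaction exactly only in a fully interacted model, and the √2 ratio assumes a similar type mix and variance in the two arms.

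None of this supplies the missing contrast. The exploratory label excuses low power and unadjusted error rates; it does not turn a within-arm association into an estimate of effect modification.

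**Conclusion.** The point holds. The plan names the type-by-treatment interaction, sets it aside for low power, and substitutes by-arm effects that cannot answer that question and do not improve precision. No section of either document plans a between-arm contrast of the type effects.

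The risk of misreading is conditional. It depends on two-sided 5% tests and a reader who compares them, and its size depends on how prognostic aphasia type is and on the number and sizes of the type groups, which the documents do not give. It is substantial for common type effects of roughly 1 to 2 points, a range that includes the trial's 1.5-point margin. It is small when the effect is very large.

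The primary futility conclusion is untouched. This is a worthwhile correction to an exploratory analysis.

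**What to change.** **In SAP 9.2, add** one model on both arms for the change from pre-treatment to immediate post-testing, with treatment, aphasia type, treatment × aphasia type and the other covariates. If the repeated-visit scores of 9.3 are used instead, the relevant term is treatment × type × visit with its lower-order terms. In a model of scores, treatment × type alone describes differences in level averaged over visits, not differences in change.

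**Report** the interaction estimate with its 95% CI, and the tDCS-minus-sham difference by type where numbers allow, all labelled exploratory.

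**Keep if wanted** the by-arm type effects and Spearman correlations as descriptive summaries, with a statement that their p-values will not be compared between arms. Align 9.3 and protocol 3.5.2 with this, and correct the reference to section 3.14.

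**Cost.** No new data: aphasia type is already collected and used in randomization (protocol 3.2, SAP 6), and SAP 2 foresees an update before database lock. The statistical price is a wide interval (Step 4), which shows the precision the trial has. Sparse types may have to be combined; that grouping should be fixed before unblinding.
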